	3			DU	DU	D	D	D	D	S	S
	4				DU	DU	DU	D	D	D	D
	5					DU	DU	DU	DU	DU	D
	6						DU	DU	DU	DU	DU
	7							DU	DU	DU	DU
	8								DU	DU	DU
	9									DU	DU
	10										DU

E: Escalate to the next higher dose, S: Stay at the current dose, D: De-escalate to the previous lower dose, DU: De-escalate to the previous lower dose and the current dose will never be used again because of unacceptable high toxicity.

Note: a total of at least 6 participants are evaluable for DLT in a specific cohort, safety data for these participants will be reviewed by the Study Board to determine if the dose needs to be reduced.

Dose limiting toxicity: Selected events occurring during the DLT observation period (defined in the individual substudy) are considered as DLT unless due to disease progression or to a cause obviously unrelated to SAR444245. Please refer to the full list of events as below. Based on the occurrence of DLT and overall assessment of safety data supplemented with data from other SAR444245 studies, the Study Board will determine if the dose of SAR444245 needs to be reduced to █ μg/kg or another lower dose level, in agreement with the Sponsor.

Hematologic abnormalities:

- Grade 4 neutropenic fever (temperature $\geq 38.5^{\circ}\text{C}$ on more than 1 occasion).
- Grade 4 thrombocytopenia associated with clinically significant bleeding requiring clinical intervention.

Non-hematologic abnormalities:

- Grade 3 or above alanine aminotransferase (ALT) or aspartate aminotransferase (AST) in combination with a bilirubin $> 2 \times$ upper limit of normal (ULN) with no evidence of cholestasis or another cause, such as viral infection or other drugs.
- Grade 3 or above vascular leak syndrome (VLS)
- Grade 3 or above hypotension

- Grade 3 or above cytokine release syndrome
- Grade 3 or above AE that does not resolve to grade ≤ 2 within 7 days of starting accepted standard of care medical management.
- The following non-hematologic AEs are exceptions that are not considered DLTs:
 - Grade 3 or 4 laboratory abnormalities that are not clinically significant per recruiting Investigator and Sponsor will not be considered a DLT.

Study Board

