4.3 JUSTIFICATION FOR DOSE

Dose escalation for SAR444245 monotherapy and in combination with pembrolizumab or cetuximab is ongoing in the first-in-human HAMMER study. Data from a total of 68 patients who have received SAR444245 Q2W or Q3W in monotherapy, in a Q3W regimen in combination with pembrolizumab 200 mg Q3W, or with cetuximab 400/250 mg/m² QW is available as of 18 June 2021. HAMMER Safety Review Committee have cleared SAR444245 24 µg/kg Q3W pembrolizumab combination dose level based on this data cut-off.

The dose levels tested to date for SAR444245 monotherapy administered using a Q3W schedule are 8 µg/kg (n=4), 16 µg/kg (n=6), 24 µg/kg (n=11), 32 µg/kg (n=6) and 40 µg/kg (n=2).

In combination with pembrolizumab, SAR444245 has been administered Q3W at the doses of 8 µg/kg (n=4), 16 µg/kg (n=9), 24 µg/kg (n=6), 32 µg/kg (n=1). In combination with cetuximab, SAR444245 has been administered Q3W at 16 µg/kg (n=5) or 24 µg/kg (n=5).

For monotherapy cohort, the only DLT observed to date is a Grade 3 infusion reaction (occurred on C2D1 which resolved on the same day with supportive care) reported in a patient on 32 µg/kg Q3W monotherapy.

For SAR444245 in combination with pembrolizumab 200 mg Q3W, 1 DLT (Grade 3 liver enzyme elevation with Grade 2 bilirubin elevation meeting drug-induced liver injury [DILI] criteria occurred on C1D1 which resolved after 7 days with steroids) was observed in a participant with SAR444245 24 µg/kg Q3W with pembrolizumab.

No DLTs were reported by SAR444245 cetuximab combination cohort (SAR444245 24 µg/kg Q3W).

Grade 3/4 TEAEs commonly reported by participants who received SAR444245 24 µg/kg monotherapy (n=11) include in particular Grade 4 lymphocyte count decreased/lymphopenia (7 participants, 63.6%) and Grade 3 anemia (3 participants, 27.3%) and Grade 3 dyspnea (2 participants, 18.2%). Of note, transient lymphocyte count decrease in the peripheral blood is an expected effect, consequence of T cell activation and temporary compartmental redistribution after IL-2 treatment. Nevertheless, this phenomenon is reported as an adverse event (AE) in HAMMER study.

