- a Blood Chemistry/hematology should be done with an overnight fasting if possible (should not interfere with hydration requirements). It will be performed weekly on D1 pre-dose, D8 and D15 (D15 for participants who receive Q3W only) during Cycle 1, then on Day 1 of every cycle up to Cycle 12, then every other cycle during Treatment Phase. Visits and assessments on C1D2-D3 will be performed for participants in the safety run-in or participants who are hospitalized because of high tumor burden or at Investigator's discretion. During the Observation Period, it will be performed at Follow-Up Visit 1. It can also be performed as clinically indicated. In case of Grade ≥ 3 liver function abnormal tests, additional tests will be repeated every 2-3 days until recovery to baseline value.
- b Modification of Diet in Renal Disease (MDRD) equation: Glomerular filtration rate (mL/min/1.73 m²) = 175 × (Serum Creatinine)-1.154 × (Age)-0.203 × (0.742 if Female) × (1.212 if African American)
- c Bicarbonate or carbon dioxide (venous) (if bicarbonate or carbon dioxide are assessed only on arterial blood at site level, to be done only if clinically indicated)
- d Endocrine function tests will be performed every 2 cycles throughout the entire treatment period and at EOT. During the Observation Period, they will be performed at Follow-Up Visit 1. They can also be performed as clinically indicated.
- e Pregnancy Test: Women of childbearing potential must have a negative urine pregnancy test result within 72 hours prior to first IMP administration of each cycle, at EOT and every 30 (± 7) days until 120 days (or refer to the individual substudy protocol) after the last dose of study treatment. If urine pregnancy results cannot be confirmed as negative, a serum pregnancy test will be required. Pregnancy tests (serum and/or urine tests) should be repeated if required by local guidelines.

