Intervention groups and duration:

Please refer to the master protocol for common descriptions of the study duration. For Cohort C1, the maximum cycles allowed are 52 cycles.

Study interventions**Cohort C1: DLBCL participants with stable disease or progressive disease 1-3 months after receiving a Health Authority approved CAR-T as at least 3L therapy**

Dosing sequence: premedication for SAR444245 (30 to 60 minutes prior to start of SAR444245 infusion), and SAR444245.

Investigational medicinal products

SAR444245

SAR444245 formulation and route of administration as described in the master protocol.

- Dose regimen: 24 µg/kg administered (or reduced to █ µg/kg or another lower dose level recommended by Study Board) as an IV infusion over 30 minutes every 2 weeks on Day 1 of each cycle (14 days per cycle) for **up to 52 cycles**.

Non-investigational medicinal products

Please refer to the master protocol.

Statistical considerations:

Please refer to the master protocol for descriptions of common statistical considerations. Substudy-specific analyses are summarized below.

[figure not shown]
- **Analysis of primary endpoint:**
 - The objective response rate (ORR) will be summarized for the efficacy population with descriptive statistics. In addition, two-sided 90% CIs for ORR will be computed using the Clopper-Pearson method.
- **Analysis of secondary efficacy endpoints:**
 - The complete response rate (CRR) will be summarized for the efficacy population with descriptive statistics. In addition, two-sided 90% CIs for CRR will be computed using the Clopper-Pearson method.

Data Monitoring/Other Committee: Yes

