a Evaluation: Screening assessments to be performed prior to first IMP administration unless otherwise indicated. Baseline evaluations should be completed within 7 days prior to the first dose of IMP, except for tumor assessment that may be performed within 28 days prior to IMP administration, and unless specified otherwise. There is no need to perform Cycle 1 Day 1 laboratory assessments that have been performed as part of screening within 3 days prior to first IMP administration. During the study treatment period, all assessments must be performed, and results should be reviewed by the investigator **prior to IMP administration** at that visit. After Cycle 1, samples for laboratory assessments (excluding PK & biomarker) can be collected up to 2 days prior to IMP administration. ICF must be signed before any study-specific procedures are performed and can be signed more than 28 days prior to first IMP administration. Screening time indicates the maximum time frame relative to the first IMP administration in which study procedures used to support eligibility are done.

- b Cycle: A treatment cycle is 14 days. See details in [Section 6.1](#) for IMP administration. If treatment cycles are adjusted, all procedures except tumor assessment imaging will be completed according to the Cycle number. Tumor assessment imaging will be performed at fixed time points from C1D1 regardless of any treatment delays.
- c Observation Period: Participants who enter the Observation period will be followed differently depending on the reason leading to permanent study treatment discontinuation. See Section 4.1 of the master protocol. For participant's convenience, all Follow-up assessments may occur during the same visit as that when tumor assessment is performed.
- d Survival Phone Call Follow-Up Period: Once the participant stops the tumor assessments due to PD or starts a new antineoplastic therapy, the participant moves into the Survival Follow-up Period and should be contacted by telephone approximately every 3 months \pm 14 days to assess for survival status. Updated survival status may be requested by the Sponsor at any time during the study.
- e Visits on C1D2, D3 are for safety-run in participants only.

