- f C1D8 visit must be performed on site only for participants enrolled in the Safety run-in and participants scheduled to have blood draws for biomarker assessment on Day 8. For all other participants, this on-site visit may be done remotely as appropriate based on Investigator's discretion per institutional standard and local regulations. If this is the case, this must be documented in the source document. Study Board may decide to cancel safety assessment on C1D8, upon agreement with Sponsor, if safety data justify it.
- g Weight/Height: Height is required at baseline only for patients > or =18 years old. For trial participants <18 years old, height should be assessed on day 1 \pm 1 of each cycle. Weight is required at Screening and prior to starting each infusion. The total dose will be calculated based on the weight on the day of the infusion or the most recent weight assuming it was assessed in a reasonable time frame according to Investigator assessment. Study sites should make every effort to measure body weight as close to the infusion day as possible considering the variability of local process from site to site. If the infusion is prepared with the most recent weight assessed in a reasonable time frame, this will not prevent to assess the weight on D1 of each cycle.
- h Blood chemistry/ hematology will be performed weekly on D1 pre-dose and D8 during Cycle 1, then on Day 1 of every cycle up to Cycle 24, then every other cycle during Treatment Phase. Visits and assessments on C1D2-D3 are only for participants in the safety run-in or participants who are hospitalized because of high tumor burden or at investigator's discretion. For these participants, vital signs, SpO₂ and complete blood counts (CBC) and differentials, chemistries (blood urea nitrogen (BUN), creatinine (Cr), alanine transaminase (ALT), aspartate transaminase (AST), alkaline phosphatase (Alk Phos), total bilirubin (TBil) will be obtained daily.
- i Tumor lysis laboratory tests (corrected calcium, magnesium, phosphate, uric acid, and lactate dehydrogenase [LDH] levels) will be obtained every 8 hours on C1D1 for safety run-in participants or participants who are hospitalized, and C1D2-D3 for safety run in or participants who are hospitalized because of high tumor burden or at Investigator's discretion.

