4 STUDY DESIGN

4.1 OVERALL DESIGN

This substudy will include approximately 25 participants with diffuse large B cell lymphoma (DLBCL) who have received at least 2 lines of systemic therapy and have either stable or progressive disease 1-3 months after receiving a Health Authority approved CAR-T therapy. The substudy will assess SAR444245 monotherapy as at least 3rd line of therapy.

Please refer to the master protocol for a full description of the study design, and for details applicable to all therapy cohorts.

A graphical presentation of the study schema is shown in [Figure 1](#).

The dose-limiting toxicity (DLT) observation period is 28 days for Cohort C1. The maximum cycles allowed in this substudy for Cohort C1 are 52 cycles.

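### Cohort C1: the 28-day DLT window covers two doses but requires no safety laboratory panel after the second, so a transient, asymptomatic laboratory DLT can go unseen at dose confirmation

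*Protocol*

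**What the plan says.** Substudy 03, Section 4.1: "The dose-limiting toxicity (DLT) observation period is 28 days for Cohort C1". Section 1.3, footnote b: "A treatment cycle is 14 days", with SAR444245 given on Day 1 of each cycle (Section 1.1). SAP Section 3.9 records that the window was lengthened from 21 days to 28 days (2 cycles) to match the 2-weekly schedule.

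The laboratory timing stands in two places:
- Substudy 03, Section 1.3, footnote h: chemistry and hematology are "performed weekly on D1 pre-dose and D8 during Cycle 1, then on Day 1 of every cycle up to Cycle 24". Safety run-in participants also have panels on Days 2 and 3 of Cycle 1.
- Master protocol, Section 10.2, Table 6 footnote a: "D8 and D15 (D15 for participants who receive Q3W only) during Cycle 1, then on Day 1 of every cycle up to Cycle 12". The extra Day 15 panel in Cycle 1 is thus for 3-weekly dosing only.

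Footnote a of the Substudy 03 schedule requires assessments to be done and reviewed before dosing, and adds: "After Cycle 1, samples for laboratory assessments (excluding PK & biomarker) can be collected up to 2 days prior to IMP administration". The Day 1 visit itself has a window of ±2 days.

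Among the DLTs in master protocol Section 4.1 is Grade 3 or higher ALT or AST together with bilirubin above 2 × ULN. It carries no minimum duration.

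**The concern.** A DLT window of two cycles is there to observe two doses. After dose 1 the run-in schedule looks for laboratory toxicity on Days 2, 3 and 8, and again on Day 15 before dosing. After dose 2 it requires nothing until a sample that nominally falls one day after the window closes.

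A participant counts as DLT-evaluable once the window has been observed. For dose 2, a DLT-free classification could therefore rest on no laboratory data at all. The documents also do not say whether an abnormality first seen at Cycle 3 Day 1, on or after Day 29, counts as a DLT. At stake is the Study Board's decision to keep 24 µg/kg every 2 weeks for the rest of the cohort.

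**Working it through.** **Calendar.** Inputs: 14-day cycle, dosing on Day 1 of each cycle, 28-day window (Substudy 03, Sections 1.1, 1.3 and 4.1).
- Window: 2 × 14 = 28 days, which reproduces the plan's figure.
- Day 1 of cycle k falls on study day 1 + 14(k − 1). Cycle 2 Day 1 = Day 15, Cycle 2 Day 8 = Day 22, Cycle 3 Day 1 = Day 29.
- Run-in panels: Days 1, 2, 3, 8, 15 (before dose 2) and 29 (before dose 3).
- Panels after dose 2 and by Day 28: 0. Days without a panel: 16 to 28, that is 13 of 28.

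**Permitted timing.** With dose 2 on Day 15, dose 3 may be given on Days 27 to 31 and its sample drawn 0 to 2 days earlier, so on Days 25 to 31. Of the 5 × 3 = 15 combinations of dose day and sampling lead, 9 put the sample on or before Day 28. This is a count of what is allowed, not a probability. Days 16 to 24 have no scheduled panel under any of them.

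**If Cycle 3 is not started.** The next scheduled panel may be the end-of-treatment visit, 30 ± 7 days after the last dose: 15 + 30 ± 7 = Days 38 to 52, or earlier if further therapy begins.

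**Comparison.** Cohort A has one dose in a 21-day window, with panels on Days 8 and 15, although its Study Board may cancel the Day 15 safety assessment (Substudy 01, Section 1.3, footnote f).

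**Effect on the dose rule** (master protocol, Table 2). E and S both mean continuing at 24 µg/kg; D and DU mean a lower dose.

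| Evaluable | Last count that continues | First count that de-escalates |
|---|---|---|
| 6, 7 or 8 | 2 (S) | 3 (D) |
| 9 or 10 | 3 (S) | 4 (D) |

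Recomputing the decisions from the intervals in Section 4.1 reproduces Table 2 for 6 to 10 participants. I assumed a Beta(1,1) prior, and DU when the posterior probability of a rate above 0.3 exceeds 0.95; the documents state neither.

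**Illustration.** Let p be the true DLT rate and f the share of DLTs that go unseen. The chance of a de-escalation call is P(X ≥ r), with X ~ Binomial(n, p(1 − f)). The documents give no value for f, so 0 to 30% is an assumed range.

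| p | n, r | f = 0 | f = 10% | f = 20% | f = 30% |
|---|---|---|---|---|---|
| 0.30 | 6, 3 | 25.6% | 20.2% | 15.4% | 11.2% |
| 0.30 | 10, 4 | 35.0% | 27.3% | 20.1% | 13.9% |
| 0.40 | 6, 3 | 45.6% | 37.3% | 29.4% | 22.0% |
| 0.40 | 10, 4 | 61.8% | 51.3% | 40.4% | 29.8% |

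Only part of the DLT list can be missed in this way, so the upper end of f should not be read as an estimate.

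**The case against.** The plan has other ways of finding such events. Unscheduled samples for safety are allowed (master protocol, Sections 8 and 10.2). The Cycle 3 Day 1 panel must be reviewed before dose 3, so it would show any abnormality that persists, and Grade 3 or higher liver abnormalities then trigger repeat tests every 2 to 3 days. That panel may also fall inside the window. All of this stands. It does not reach an asymptomatic abnormality that rises and falls between visits, and nothing requires the panel to be early.

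A reader might infer that laboratory DLTs in general go undetected after dose 2. The list in Section 4.1 does not support that:
- Neutropenic fever needs repeated fever, and thrombocytopenia counts only with clinically significant bleeding; both present clinically.
- Laboratory abnormalities judged not clinically significant are excluded.
- The general criterion, "Grade 3 or above AE that does not resolve to grade" 2 or lower within 7 days of starting management, concerns events that persist.

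What remains is chiefly the ALT/AST-with-bilirubin criterion.

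A reader might also infer that one unseen DLT reverses the dose decision. That needs exactly two other counted DLTs with 6 to 8 participants, or three with 9 or 10. Table 2 also applies only unless the Study Board decides otherwise, and the Board weighs overall safety data and other SAR444245 studies.

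The earlier clinical experience gives limited support. For monotherapy, "the only DLT observed to date is a Grade 3 infusion reaction (occurred on C2D1" at 32 µg/kg every 3 weeks, but that is a clinical event which needs no panel to detect. The liver DLT in Section 4.3 occurred with pembrolizumab under the first dose. It shows only that such an event can be transient, since it resolved after 7 days with steroids. In the primate study (Table 8), clinical pathology changes were generally most marked 3 days after each dose, which after dose 2 would be Day 18. However, Table 8 reports no liver findings of this kind in primates.

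**Conclusion.** The point holds in a limited form. The Cohort C1 window was set at two cycles, but the laboratory schedule requires no panel after dose 2 within it: 0 panels in 13 nominal days, and none in Days 16 to 24 under any permitted timing. An asymptomatic, transient laboratory DLT, chiefly the liver criterion, can therefore be missed at dose confirmation. The status of an abnormality first seen on or after Day 29 is undefined; read strictly, it lies outside the DLT period.

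The documents do not support the stronger conclusion that dose confirmation in this cohort is invalid, because clinical DLTs, persistent abnormalities and symptom-driven tests are still captured. The effect on the recommendation is confined to the S/D boundary.

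The calendar rests on dose 2 being given on Day 15 and on footnote h governing laboratory timing. Biomarker draws are not counted as safety panels. The gap should be closed because it bears on a dose decision made with as few as 6 evaluable participants, and closing it is cheap.

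**What to change.** Reconcile footnote h (Substudy 03, Section 1.3) and Table 6 footnote a (master protocol, Section 10.2) with the 28-day, two-dose window for Cohort C1 run-in participants, so that at least one scheduled safety panel after dose 2 informs the DLT assessment. The Day 8 visit already in the schedule for Cycles 2 to 16 is one place for it. A panel at Cycle 2 Day 8 (Day 22) would take the count after dose 2 from 0 to 1 and cut the longest nominal gap from 14 days to 7.

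Make explicit whether the Cycle 3 Day 1 pre-dose panel informs the DLT assessment, and what applies if Cycle 3 is not started. Doses and DLT criteria stay as the sponsor defines them.

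The same edit should reconcile how long Day 1 panels continue: to Cycle 12 in the master protocol, to Cycle 24 in Substudy 03. That difference does not affect the gap.

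Cost: one routine blood draw in about 6 to 10 participants at a visit already planned, and changes to two footnotes. If the Cycle 3 Day 1 panel is counted, the Study Board review may wait about a day for the result.

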1.5 PHARMACOKINETIC FLOWCHARTS

Cycle	Treatment Cycle 1					Treatment Cycle 2, 4, 7, 10 + every 5 th cycle		EOT visit	
Day	D1			D2	D3	D8	D1		30 (± 7) days after last IMP administration
Time after start of SAR444245 dosing [h]	SOI	EOI	4h post EOI	At any time	At any time	At any time	SOI	EOI	At any time
SAR444245 PK sample		P00 ^b	P01	P02 ^c	P03 ^c			P00 ^b	
SAR444245 ADA sample	AB00 ^a					AB01	AB00 ^a		ABF00

a Samples collected strictly before start of infusion (SOI). ADA sampling may be discontinued by the Sponsor once sufficient data have been collected.

b PK sample must be taken at the end of infusion (EOI) after flush.

c P02 and P03 to be collected during safety run-in and when participants are hospitalized.

In the event the infusion is interrupted, a PK sample should be drawn immediately after interruption. If infusion is not likely to be resumed by clinical assessment, subsequent samples should be drawn at 4 h after interruption. If infusion is resumed, a (further) PK sample should be drawn at end of resumed infusion and subsequent sample should be drawn at 0.5 h after end of resumed infusion. PK sampling may be discontinued by the Sponsor once sufficient data have been collected.

Abbreviations: ADA: anti-drug antibodies; D: day; EOT: end of treatment; PK: pharmacokinetic.

2 INTRODUCTION

Study ACT16941 is developed as a master protocol in order to accelerate the investigation of SAR444245 with or without various anticancer therapies by identifying early signals. The information that is common to all cohorts is included in the master protocol, and this substudy provides details specific to Cohort C1 (participants with DLBCL who have received at least 2 lines of systemic therapy and have either stable or progressive disease 1-3 months after receiving a Health Authority approved CAR-T therapy) for SAR444245 monotherapy.

Please refer to the master protocol for an introduction for ACT16941.

